It is expected that candidate vaccines will produce virus populations with low neurovirulence, and therefore it is possible that very few mice are paralyzed at the fixed dose level of inoculum (4.0 \log_{10} CCID₅₀), or at lower dose levels for either or both vaccine candidates. It is also possible that few subjects shed virus in sufficient quantity to enable the assay to be conducted. In either case, it is possible that the GLMM described above may not be able to be fitted to the data. In the event that paralysis proportions are low, the variance component will be difficult to fit. If the model is unable to be fitted using SAS default values for optimization convergence criteria, the following methods will be employed, in sequence, as backup:

1. The GLMM model will be reduced to a GLM model, by omitting the variance component term, and all methods above will be used. This method ignores the overdispersion expected by combining data from heterogeneous virus populations obtained from different subjects but will produce reliable estimates of mean paralysis rates if the contributions from each subject (sample size of mice) are relatively balanced, which is expected here. In this case, statistical inference would be affected, but the analysis is intended to be descriptive, rather than inferential.
2. In the event that 1) above fails to fit (due, for example, to *no* observation of paralysis), then all analysis will be limited to the descriptive analyses presented above equation (1)

Comparative Analysis for OPV-vaccinated subjects

In order to compare the neurovirulence of shed virus between each candidate vs the control, the following model will be fitted:

$$\text{logit}^{-1}(p_{hi}) = \beta_0 + \beta_1 I_{[h=2]} + \beta_2 I_{[sex=F]} + \delta_i \quad (3)$$

where

- h indexes virus ($h = 1$ = control vaccine [M1], $h = 2$ = candidate vaccine [M4])
- i indexes sample (subject) within levels of h
- β_0 is the overall mean log-odds of paralysis for shed virus samples for male mice, control vaccine
- β_1 is the difference in mean log-odds of paralysis between the two vaccines
- β_2 is the difference in mean log-odds of paralysis between mouse gender (females minus males)
- p_{hi} is the paralysis rate for virus source h , sample i

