- $\delta_i \sim N(0, \tau^2)$ is the subject-level random effect for shed virus, intended to capture overdispersion due to between-sample variability in the neurovirulence of each virus population, including variability in the precise titer of inoculum, and is assumed common among all vaccine groups (but estimated uniquely in models for candidate 1 vs control, and candidate 2 vs control)

In SAS/STAT software, this model may be fitted using the PROC GLIMMIX procedure. It is preferred to use METHOD = LAPLACE in the PROC GLIMMIX statement, due to better asymptotic performance of the estimators. The SAS default method for computing degrees of freedom should be utilized for statistical tests (DDFM = BETWITHIN). SAS code to fit the model defined above is given by:

```
proc glimmix data=dat method=laplace;
  class sample vsource sex;
  model x/n = vsource sex / s cl solution ddfm = betwithin;
  random intercept / subject=sample;
  lsmeans vsource sex / cl ilink oddsratio e;
run;
```

where “sample” is the sample number (e.g., subject identifier providing the sample), “x” is the number of mice paralyzed, and “n” is the number of inoculated mice available for analysis, “vsouce” is a binary categorical (class) variable denoting whether the virus source is candidate vaccine or control, and “sex” is a categorical variable indicating the sex of the mice. The dataset “dat” should contain one row for each subject (or clinical supply sample) for each mouse gender. Additional options to the SAS procedure may be necessary to obtain all necessary output.

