Model fit results should be summarized in a table, including coefficient estimates, standard errors, p-values for *t*-tests of coefficients, and 95% confidence interval (based on the *t* distribution, the default for PROC GLIMMIX) will be displayed for coefficients as well as for the variance components. For each candidate vaccine, the odds ratio (paralysis in each candidate vaccine group relative to the control group from study M1) and its corresponding two-sided 95% CI and two-sided p-value will be presented. P-values for variance components will be based on the likelihood ratio test described by Molenberghs and Verbeke [2]. Additionally, the estimated mean paralysis rate for each virus source h , \widehat{p}_h , will be obtained from the results of the SAS LSMEANS statement, and the delta method will be used to obtain the standard error, from which the 95% confidence intervals will be obtained, utilizing asymptotic normality, and truncated at (0, 1) if necessary. The odds ratio of paralysis between mouse genders, assumed common among vaccines groups, will also be presented as described for the gender-averaged probability.

As with other model-based methods above, if the model cannot be fit, remedies involve stepwise model simplification. For this model, the first simplification will be to reduce from a GLMM to a GLM via removal of the variance component. If that model cannot be fit, results will be limited to presentation of summaries described above equation (1) and augmented with the two-sided Fisher exact p-value arising from the cross-tabulation of paralyzed mice within each group, regardless of mouse gender and subject identifier, and the p-value will be regarded as approximate. If substantial imbalance in mouse availability rate is observed, additional sensitivity analyses may be added.

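### In the exploratory neurovirulence comparison with UAM1, the rule for leaving the Wald-tested model does not cover zero paralysis in the candidate arm alone, so the plan could report p near 1 where the candidate did best

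*SAP*

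**What the plan says.** The comparison is model (3) in SAP 6.7.2, under Comparative Analysis for OPV-vaccinated subjects. It is a binomial mixed model with terms for vaccine and mouse sex and a random intercept per sample. Each candidate is compared separately with UAM1.

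- **Reported result.** The SAP asks for "the odds ratio (paralysis in each candidate vaccine group relative to the control group from study M1) and its corresponding two-sided 95% CI", and says of the odds ratio that "its corresponding two-sided 95% CI and two-sided p-value will be presented". Coefficients get t-tests, and their intervals also use the t distribution. The likelihood-ratio test is named only for variance components.
- **When the model is abandoned.** The Alternate Method for Lack of Model Fit text, written for the earlier models, sets the condition: "If the model is unable to be fitted using SAS default values for optimization convergence criteria". For model (3) the first step down removes the random effect. After that, "If that model cannot be fit, results will be limited to presentation of summaries described above equation (1"), with a two-sided Fisher exact p-value over mice added and described as approximate.
- **What is expected.** The SAP expects low neurovirulence from the candidates and says "it is possible that very few mice are paralyzed at the fixed dose level of inoculum". It notes that only 2 qualifying post-dose-1 samples exist from UAM1 before amplification. It says the models will probably fail or add little, but will be attempted.

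Nothing states what happens when one arm of model (3) has no paralysed mice and the other has some.

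**The concern.** Zero paralysis in the candidate arm with some in the Sabin arm is the pattern these vaccines were designed to produce. It is plausible here: protocol 8.4.1 says the inoculum is chosen to detect reversion of Sabin-2, so some control paralysis can be expected.

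In that pattern a logistic model has no finite estimate of the vaccine effect. A Wald statistic then becomes uninformative just where the data are most favourable. An optimiser can nonetheless stop normally, because the log-likelihood is bounded and flattens out. A rule keyed to convergence would then keep the Wald result. A report could show p near 1 beside 0% against 50% paralysis, while a candidate with one paralysed mouse is shown as significantly better than Sabin.

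**Working it through.** The SAP gives no sample size, power or expected result for this comparison, so there is no figure of its own to reproduce. The check fits model (3) to constructed data.

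**Inputs from the SAP:** 2 UAM1 samples; Wald t-test and t-based 95% CI; Laplace estimation; between-within degrees of freedom, taken here as subjects minus 2.

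**Assumptions not in the documents:** 5 or 10 mice per sex per sample; 2 to 20 candidate samples; control paralysis 20%, 50% or 80%; convergence declared at a relative gradient of 1e-8, standing in for the SAS default.

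**Why the fit can converge.** With N candidate mice and none paralysed, their log-likelihood is N·log(1 − p), which rises towards 0 as p falls. Its gradient in the vaccine coefficient b is −N·p, which goes to 0, so a gradient criterion is met at some large negative b. The information is about N·p, so SE ≈ 1/√(N·p).

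**Zero paralysed: 20/40 control against 0/100 candidate (2 and 5 samples, 10 mice per sex).**
- The fit stops at b = −20.20. With control log-odds 0, p = e^(−20.20) = 1.69e-9, so N·p = 1.69e-7 and SE ≈ 2,434. The fit gave 2,438; the gap is rounding of b.
- t = −20.20/2,438 = −0.0083 on 7 − 2 = 5 df, so p = 0.994.
- The interval is exp(−20.20 ± 2.571 × 2,438), an exponent of about ±6,268: effectively 0 to infinity.

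**One paralysed: 20/40 against 1/100.**
- b = ln(1/99) = −4.595; SE = √(1/1 + 1/99 + 1/20 + 1/20) = 1.054.
- t = −4.36 on 5 df, so p = 0.007; OR interval exp(−4.595 ± 2.571 × 1.054) = 0.0007 to 0.15.

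| Control | Candidate | Samples | Wald p, 0 paralysed | Wald p, 1 paralysed | Fisher p, 0 paralysed |
|---|---|---|---|---|---|
| 20/40 | 40 mice | 2 v 2 | 0.994 | 0.075 | 7.8e-8 |
| 20/40 | 100 mice | 2 v 5 | 0.994 | 0.007 | 1.7e-13 |
| 20/40 | 200 mice | 2 v 10 | 0.994 | 0.0005 | 1.9e-18 |
| 8/40 | 200 mice | 2 v 10 | 0.995 | 0.005 | 3e-7 |

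**Over all settings with zero candidate paralysis.** All 24 GLM fits declared convergence, with Wald p from 0.992 to 0.996. For the Laplace mixed model (10 mice per sex, 5 to 20 candidate samples, control pairs at 30/50%, 20/80% or 50/90%), 7 of 9 runs declared convergence and p was 0.978 to 0.996 in all 9. The other 2 would drop to the GLM, which gives the same answer.

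**What the data can support once clustering is respected.** If both UAM1 samples show paralysis and k candidate samples show none, a permutation of whole samples has smallest p = 1/C(k+2, 2):
- k = 5: 1/21 = 0.048. k = 10: 1/66 = 0.015. These are also the two-sided values for a difference in means. Labelling both paralysed samples as candidate divides their sum by 5 or 10 instead of 2, which is less extreme.
- k = 2: 1/6 = 0.17 one-sided. The mirror labelling is equally extreme, so 2/6 = 0.33 two-sided.

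With controls at 12/20 and 8/20, the mixed-model likelihood-ratio p is 0.0009 (k = 5) and 0.0004 (k = 10), roughly 40 to 50 times smaller than the permutation values.

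**How likely zero is.** With independent mice at paralysis rate π, the chance is (1 − π)^n. For n = 100 and 200 it is 61% and 37% at 0.5%, 13% and 2% at 2%, and 0.6% and 0.004% at 5%. The documents give no rate.

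**The case against.** The strongest reply is that the SAP already has a method for sparse data. A reader might infer from the Wald calculation that the plan has nothing to offer when counts are zero. That is not so: the comparative section ends in a Fisher exact test, and the Alternate Method text gives absence of paralysis as an example of failure to fit. On one fair reading this case goes to Fisher. What stands against that reading is that the example was written for single-group models, where no paralysis means no events in the data at all. Model (3) pools two arms, and the stated condition is convergence, which separated data usually meet. Two analysts could report 0.994 or 1.7e-13 from the same mice.

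Other parts of the reply stand:
- SAS was not run, so its convergence behaviour is inferred from comparable optimisers.
- The problem needs paralysis in UAM1 mice. If neither arm has any, no difference is the right reading.
- The SAP foresees very few paralysed mice, which is not the same as none.
- The endpoint is exploratory and the models supplement the descriptive summaries. Counts and percentages by vaccine group would show 0% for the candidate, and an SE in the thousands is visibly degenerate.
- A likelihood-ratio p-value resting on two control samples would err in the other direction.

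A reader might also infer that this p-value decides one of the licensure criteria, because protocol 1.2.2.1 lists reduced reversion to virulence among them. The documents do not tie that criterion to this model. No decision rule uses the p-value, sequencing also bears on stability, and neurovirulence data may be combined with earlier studies.

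**Conclusion.** The concern holds as a gap in the fallback trigger. When some UAM1 mice and no candidate mice are paralysed, the rule as written most likely keeps a Wald p-value near 1 and an unbounded odds-ratio interval. The result is non-monotone: 0.994 with no paralysed candidate mouse and 0.007 with one, for 20/40 control mice against 100 candidate mice. The mechanism does not depend on the assumed mouse numbers; the p-values for one paralysed mouse do. The conclusion also rests on SAS accepting a separated fit as converged, which is likely but was not tested.

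It would go too far to say that the data would otherwise prove a large difference. The very small Fisher and likelihood-ratio values ignore or understate what two control samples imply; at the sample level the evidence is about 0.048 with 5 candidate samples and 0.015 with 10. Severity is minor to moderate.

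**What to change.** Add a rule to the comparative part of SAP 6.7.2:

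1. If either vaccine group has 0% or 100% of its mice paralysed, the Wald p-value and interval for the vaccine effect are not reported, whatever the convergence status.
2. In their place, lead with a two-sided exact permutation test on per-sample paralysis proportions.
3. Give a Firth-penalised or profile-likelihood odds-ratio interval, labelled approximate. Likelihood-ratio and profile results should not lead, because they are anti-conservative with two control samples.
4. Keep the Fisher p-value, labelled as a mouse-level approximation that ignores clustering by subject.
5. If neither group has any paralysis, report descriptive summaries only.

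The cost is one SAP paragraph and a few lines of code, with no new samples or assays. The price is coarseness. With 2 candidate samples the permutation p-value cannot go below 0.33 two-sided. The limits of 0.048 and 0.015 assume that both UAM1 samples survive amplification and both show paralysis. The report should state that limit beside the result.

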The Phase 2 study is designed to evaluate the safety and immunogenicity of both nOPV2 vaccines in adults before testing in young children and then infants. The primary objectives of the Phase 2 study include the general safety and immunogenicity of the two candidate vaccines, primarily based on comparison with historical data obtained in the Phase 4 study of Sabin mOPV2 for OPV-vaccinated subjects, in order to establish non-inferior immunogenicity and acceptable safety profile. Assessment of the general safety of the 2 candidate vaccines in IPV-only vaccinated subjects will be based on comparison with data from a placebo group.

The novel vaccine will eventually be licensed based on 3 criteria: a similar safety profile to the currently licensed mOPV2 of the Sabin strain, non-inferior immunogenicity, and reduced reversion to virulence.

The Phase 2 study will include both OPV-vaccinated and IPV-vaccinated adults to provide safety and immunogenicity data relevant to the decision to advance to future studies with testing in children who have not been exposed to OPV2.

1.2.2.2 *SEQUENTIAL TESTING OF STUDY VACCINES*

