If sufficient quantities of EES and, among them, sufficient mouse paralysis is observed, model-based analyses will be used to supplement the descriptive summaries described above. (See also the section *Alternate Method for Lack of Model Fit*, below.) It is currently known that, prior to the amplification step required to conduct the assay, only 2 post-dose-1 EES are available from the historical control subjects, UAM1. It is therefore likely that model-based analyses will fail, and/or will fail to provide additional insight beyond the descriptive summaries previously described, however, model-based analyses will still be attempted.

For each vaccine group, a generalized linear mixed model (GLMM) will be fitted to the binomial count of paralyzed mice for NEARs obtained at the $4.0 \log_{10} \text{CCID}_{50}/\text{g}$ dose level. This model is given by

$$\text{logit}^{-1}(p_i) = \beta_0 + \beta_1 I_{[\text{sex}=\text{F}]} + \delta_i \quad (1)$$

where

- β_0 is the overall mean log-odds of paralysis for male mice
- β_1 is the difference in mean log-odds of paralysis between mouse gender (females minus males)
- p_i is the paralysis rate for sample (subject) i
- $\delta_i \sim N(0, \tau^2)$ is the subject-level random effect, intended to capture overdispersion due to between-sample variability in the neurovirulence of each virus population, including variability in the precise titer of inoculum

In SAS/STAT software, this model may be fitted using the PROC GLIMMIX procedure. It is preferred to use METHOD = LAPLACE in the PROC GLIMMIX statement, due to better asymptotic performance of the estimators. The SAS default method for computing degrees of freedom should be utilized for statistical tests (DDFM = BETWITHIN). SAS code to fit the model defined above is given by:

```
proc glimmix data=dat method=laplace;
  class sample sex;
  model x/n = sex / cl solution ddfm = betwithin;
  random intercept / subject=sample;
  lsmeans sex / ilink;
run;
```

where “sample” is the sample number (e.g., subject identifier providing the sample), “x” is the mouse gender-specific number of mice paralyzed, “n” is the mouse gender-specific number of

inoculated mice available for analysis, and “sex” captures the mouse gender. The dataset “dat” should contain one row for each subject, for each mouse gender. Additional options to the SAS procedure may be necessary to obtain all necessary output.

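### The fallback neurovirulence comparisons treat mice given the same stool sample as independent, so their p-values can be far too small when paralysis clusters by sample

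*SAP*

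**What the plan says.** The relevant text is all in SAP 6.7.2.

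- **Main model.** The comparison of each candidate with UAM1 is a logistic mixed model with a random effect for each sample, "intended to capture overdispersion due to between-sample variability in the neurovirulence of each virus population, including variability in the precise titer of inoculum". It reports an odds ratio with a two-sided 95% CI and p-value.
- **First fallback.** If that model cannot be fitted, "the first simplification will be to reduce from a GLMM to a GLM via removal of the variance component".
- **Second fallback.** If the simpler model cannot be fitted either, the descriptive summaries are supplemented by a "two-sided Fisher exact p-value arising from the cross-tabulation of paralyzed mice within each group, regardless of mouse gender and subject identifier". The only caveat attached to this result is that it counts as approximate.
- **Control data.** Under Model-based Analyses the SAP reports that, before the amplification step, "only 2 post-dose-1 EES are available from the historical control subjects, UAM1". It expects that modelling will probably fail, or add nothing to the descriptive summaries, or both.
- **Caveat on dropping the random effect.** Under Alternate Method for Lack of Model Fit, the SAP says of the reduced model: "This method ignores the overdispersion expected by combining data from heterogeneous virus populations obtained from different subjects". It adds that "statistical inference would be affected, but the analysis is intended to be descriptive, rather than inferential".

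**The concern.** Each subject with a tested sample is expected to contribute one assay result at the single dose level. The mice in that result all receive virus from the same stool sample. The independent unit for comparing vaccines is therefore the sample, and the random effect in the main model recognises this. Both fallbacks remove that protection just when data are sparse. Fisher's test on pooled mice, and the standard errors of the model without the random effect, count every mouse as separate evidence. Yet the control arm may rest on two samples.

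The word approximate does not tell a reader that, under clustering, the error runs towards a p-value that is too small.

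Protocol 1.2.2.1 lists three criteria for eventual licensure: a similar safety profile, "non-inferior immunogenicity, and reduced reversion to virulence". An extremely small p-value resting on one control subject's sample could be read as strong evidence on the third.

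**Working it through.** **Inputs.** From SAP 6.7.2: two control samples (post-dose-1, before amplification), one assay result per sample, and a two-sided Fisher test on pooled mice. The documents do not give the number of mice per sample (m), the number of candidate samples (k), the paralysis rate or the between-sample variation, so these are assumed. The plan states no error rate or power for this test, so there is no figure to reproduce.

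**1. A worked case.** Take m = 20 and k = 10, which gives 2 × 20 = 40 control mice and 10 × 20 = 200 candidate mice. Suppose one control sample paralyses 10 of 20 mice and every other sample none.

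- Pooled Fisher: 10/40 v 0/200. Since no candidate mouse is paralysed, p = C(40,10)/C(240,10) = 5.9e-9.
- Sample as unit: permute the vaccine labels over the 12 samples. The difference in mean proportions is 0.25 if the affected sample falls in the control arm and 0.05 in absolute value if it falls in the candidate arm. The two-sided p is the chance that it falls in the control arm, 2/12 = 0.17.
- If both control samples are at 50% (20/40 v 0/200), pooled p = 1.9e-18 and the sample-level p is 1/66 = 0.015.

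**2. Smallest attainable sample-level p** with two controls is 1/C(k+2, 2):

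| k | Splits | Smallest p |
|---|---|---|
| 3 | 10 | 0.10 |
| 5 | 21 | 0.048 |
| 10 | 66 | 0.015 |
| 20 | 231 | 0.0043 |

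**3. Type I error if pooled Fisher is always run** (nominal 5%, no vaccine difference).

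- Beta-binomial samples, m = 20, 2 v 10, paralysis 10–20%: 20–23% at within-sample correlation 0.1 and 38–46% at 0.3. At 5% paralysis: 14% and 24%.
- Logit-normal sample effects with SD τ, m = 20, k = 5 to 20: with τ = 1, about 5–6% at 2% paralysis, 12–13% at 5% and 29–30% at 20%. With τ = 2: 25–28%, 40–43% and 51–53%.
- No between-sample variation (τ = 0): 0.3–4.2% over the values of m, k and paralysis tried, so valid or conservative.

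**4. Type I error given that Fisher is reached.** Fisher is used only when the model without the random effect cannot be fitted. That was taken to mean separation: no paralysis, or no unparalysed mouse, in a vaccine arm, or no paralysis in one mouse sex. Beta-binomial, m = 20, 2 v 10, correlation 0 to 0.3:

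- 2% paralysis: reached in 51–87% of runs; error then about 0.7–8%.
- 5% paralysis: error then about 0.5–19%.
- 10–20% paralysis: reached in about 1–10% of runs at correlation 0.1 and 9–31% at 0.3; error then over 50%.

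The logit-normal model, with separation by vaccine arm only, gives higher conditional error at 5% paralysis: 18–28% at τ = 1 and 54–83% at τ = 2. The result is sensitive to the form of clustering assumed.

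If no mouse is paralysed in either arm, p = 1.

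**5. The first fallback.** A Wald test without the random effect (mouse sex omitted), among beta-binomial runs where it can be fitted, with m = 20, 2 v 10 and 10–20% paralysis, rejects in 16–23% at correlation 0.1 and 32–42% at 0.3.

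**The case against.** A reader might infer that the Fisher p-value will always be far too small, and that the SAP regards Fisher as its likely route. The documents support neither.

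- **Size.** Every driver is an assumption, with the assay details left to an SOP outside the documents. The SAP anticipates that very few mice may be paralysed. In that setting, with little clustering, Fisher is about right or conservative.
- **Trigger.** Error rates that assume Fisher is always run do not describe its use after two models have failed. Where its conditional error is highest in the beta-binomial runs, it is reached less often.
- **Likelihood.** The SAP says that models may fail or may add no insight. It does not say that the Fisher step is likely.
- **Disclosure.** The SAP admits that dropping the random effect affects inference, and calls the Fisher p-value approximate. Its listings and boxplots show paralysis by sample, so a reader could see that a difference rests on two controls.
- **Importance.** Neurovirulence is exploratory, has no success rule, and nothing makes this p-value a decision input. Sequencing has its own analysis document.

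These points stand, and they limit the size and weight of the problem. They do not remove it. The descriptive-only remark is made about the within-group models. The comparative section still asks for an odds ratio, CI and p-value, and neither caveat states the direction of the error.

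**Conclusion.** The defect is real but conditional, and minor. Both fallbacks ignore clustering that the SAP itself expects. The resulting p-values can be wrong by many orders of magnitude when paralysis concentrates in one or both control samples. How often that would happen cannot be settled from the documents, because mice per sample, candidate samples, paralysis rate and clustering are not given. The count of two controls may also change, since it covers post-dose-1 samples before amplification. What the documents do settle is that the unit of analysis is wrong and that the reader is not told which way the p-value errs.

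**What to change.** In the comparative part of SAP 6.7.2:

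1. Replace the pooled Fisher p-value with an exact permutation test of sample-level paralysis proportions, permuting vaccine labels over samples, and state the smallest attainable p for the numbers actually tested. Where that value exceeds 0.05 (for example 2 v 3 samples), report no p-value.
2. When the model without the random effect is used, report point estimates only, and take any p-value from the same sample-level test.

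The cost is a few lines of SAP text and a short program, with no new data. The drawback is little power with two control samples, which reflects the information available. If the sponsor prefers to keep the pooled p-value, the least change is a sentence saying that it is too small when paralysis clusters by sample.
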